### 1.2 *State the hypotheses to be tested, if applicable.*

**Response:** . The first two studies are developmental and exploratory, and intended to be lay the foundation for the development and testing of the FMI intervention. Thus, no specific hypotheses are forwarded. For the third study, we do have hypotheses about how women will respond to our intervention. We expect changes in readiness and other barriers to be associated with implementation of FAPBs. We will also use our follow-up data to provide a rich description of the role of alcohol in implementing FAPBs, and whether the FMI reduces the impact of alcohol use. In exploratory analyses, we will examine how the FMI intervention may be associated with decreased assault risk, as well as decreased drinking.

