**Stage 3: Intervention Testing**

**Aim 3.** Conduct a mini-trial with 3-month follow-up via weekly assessments to examine changes in target attitudes (readiness, barriers) and behaviors (friend-based assault prevention behavior skills). We also will examine knowledge and strategies pertaining to the role of alcohol in helping behavior, and will test whether drinking influences the implementation and efficacy of this intervention.

Twenty-four friend dyads will participate in the FMI along with 24 wait-list control dyads (total of 48 dyads). We will compare groups on outcomes at post-intervention and at bi-weekly 3 month follow-ups, and also examine within subjects change. Given the pilot nature of the R34 mechanism and the smaller sample size, we will focus on whether effects are in the expected direction and whether the strength of effect sizes are of practical magnitude. We expect participants receiving the FMI to demonstrate significant increases in readiness, and engagement in FAPBs and alcohol strategies, and decreases in perceived barriers (improved self-efficacy, relationship concerns), at post-intervention and over the 3-month follow-up. We will also use our follow-up data to provide a rich description of the role of alcohol in implementing FAPBs, and whether the FMI reduces the impact of alcohol use. In exploratory analyses, we will examine whether the intervention may be associated with decreased assault risk, as well as decreased drinking (see **Data Analysis Plan**).

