### **Instruments & Measures (For Stage 3)**

Data collection will occur at baseline and bi-weekly assessments, and a final evaluation that will be administered at the end of the last bi-weekly assessment. At baseline, we will collect demographic data, as well as drinking and sexual victimization history, and descriptive information regarding the relationship of the friends in our dyads. Other self-report measures will be administered both at baseline and then weekly during the follow-up periods (as denoted below). In the final (exit interview) evaluation, we will obtain feedback on participants' perceptions of the intervention and potential iatrogenic effects. All self-report measures may be completed prior to the session.

The proposed intervention will be designed to use relationship and responsibility in friend dyads as the basis for decreasing perceived barriers to intervention, improving readiness for helping friends, increasing knowledge about alcohol's effects on helping and strategies for overcoming or working around these effects, and imparting friend-based helping skills. These attitudes and behaviors will be the target intervention outcomes. Sexual assault will be examined as a secondary outcome. Changes in drinking also will be examined though this is not the principal focus of the intervention.

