#### *16.2 If applicable, provide a power analysis.*

**Power Estimates and Sample Size.** This is an intervention development project. As such, the focus is on feasibility rather than on statistical significance. For this reason, as described above, our analyses will focus largely on the derivation of effect sizes to inform parameter estimates for future studies, and to gauge clinical significance of the intervention. Still, we will conduct inferential tests. For these, with a sample of 88 in Study 3, we will be powered to detect “moderate” to “large” intervention effects.

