*Outcome analyses.* The primary goals of Aim 3 are to evaluate whether (1) FMI increases readiness and reduces perceived barriers to intervene, and increases alcohol knowledge and strategies post-intervention and over the follow-up (2) FMI increases the implementation of friend-based assault-protective behaviors (FAPB) in our 3-month follow-up, and (3) changes in readiness and perceived barriers for protective behaviors, and alcohol knowledge and strategies are associated with implementation of FAPDs at 3-month follow-up (potential mechanisms). We will also examine if quality of the dyad relationship changes as a function of the intervention. Increases or decreases in relationship quality as a function of the intervention would suggest either a positive impact on dyadic relationships or iatrogenic effects of the intervention, respectively. Whether increases in implementation of behavioral strategies are associated with reduced rates of sexual victimization will also be examined. Examination of sexual victimization is exploratory, as victimization rates are expected to be relatively low over the short follow-up period (i.e., approx. 30% across 3 months; Parks et al., 2008). In secondary analyses, we will also consider alcohol use as an outcome variable to examine potential intervention effects on drinking. Given the pilot nature of the R34 mechanism and the smaller sample size, we will focus analysis on effect sizes and whether effects are in the proposed direction. Effect size estimates can be unreliable in small pilot studies (Kraemer et al., 2006); thus, we will report effect sizes ranges (95% confidence bands).

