A prominent feature of our design is that individuals are nested within dyads, and this necessitates a data analytic approach that can accommodate nested data structures. Hence, our Aim 3 analyses are built around hierarchical linear models (HLMs). First, we will evaluate group differences on variables from our first post-intervention assessment (i.e. perceived barriers, readiness, alcohol knowledge and strategies, and implementation of FAPBs) using a two level model (individuals nested within dyads). Treatment will be dummy coded (FMI vs. waitlist control group) and included as a level two covariate. Second, we will utilize all data from our three month follow-ups and repeat these analyses using a three-level model (6 repeated measures nested within individuals, and individuals nested within dyads). In these models treatment will be included as a level three covariate. We will use  $\beta$  to describe effect sizes (Cohen, 1988; Selya et al., 2012).

Our burst design provides a rich opportunity to examine whether changes in target constructs of interest (e.g., barriers, skills, alcohol knowledge and strategies) are associated with implementation of FAPBs. For these analyses we will combine the post-intervention data from our FMI and WLC groups after the latter has completed the intervention and follow-up assessments. Combining groups will increase our sample size and provide more stable estimates of effect sizes. For these analyses we will include reports of past week protective behavioral strategies just prior to the intervention and weekly aggregates of variables of interest from our three-month follow-up yielding 7 repeated measures nested within individuals and individuals nested within dyads. Time will be included as a level-1 covariate, and we will

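### Four or five unranked primary-goal constructs, inferential tests planned, and no primary contrast or error control: about an 11–23% chance of a false significant result on the contrasts the control schedule supports

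*Combined protocol and SAP*

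**What the plan says.** The SAP's outcome analyses open with three goals of equal rank: "The primary goals of Aim 3 are to evaluate whether (1) FMI increases readiness and reduces perceived barriers to intervene", together with alcohol knowledge and strategies; whether it raises FAPB implementation; and whether changes in the former are associated with the latter. Protocol section 10.3 treats the same set as joint targets: "These attitudes and behaviors will be the target intervention outcomes". Only sexual victimisation (exploratory) and alcohol use (secondary) are ranked lower as outcomes.

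Each construct is compared between arms first in a two-level model at the first post-intervention assessment. Then: "Second, we will utilize all data from our three month follow-ups and repeat these analyses using a three-level model".

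On inference the plan points two ways. The SAP says "we will focus analysis on effect sizes and whether effects are in the proposed direction" and "we will report effect sizes ranges (95% confidence bands". Section 16.2 likewise puts feasibility ahead of significance, but continues "Still, we will conduct inferential tests" and describes the sample as powered for moderate to large effects. Aim 3 in section 4 says "We expect participants receiving the FMI to demonstrate significant increases in readiness, and engagement in FAPBs and alcohol strategies". No alpha, sidedness, ordering or adjustment appears anywhere.

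Two measurement rules bear on the number of contrasts. The Stage 3 procedures assess wait-list dyads at baseline and at 12 weeks only, before they receive the FMI. Section 10.3 measures alcohol knowledge at baseline, post-intervention and 12 weeks, and only the strategies bi-weekly.

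**The concern.** The contrasts can disagree. Readiness might rise straight after the session while FAPB implementation is unchanged at three months, and the plan does not say which result would show that the FMI did what it was meant to do. With several nominal 5% tests under equally ranked goals, a chance finding on any of them could be reported as meeting a primary goal.

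The same freedom affects estimation. Section 16.2 says the effect sizes are meant to supply parameter values for later studies. If no contrast is named beforehand, the most favourable of several noisy estimates can become the planning value for the next trial.

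The choice of score is open too. FAPB is covered by two instruments, one with four subscales, each answered for help given and for help received. Readiness is covered by a ruler and three Decisional Balance scores. Section 10.3 labels no instrument as the measure of perceived barriers.

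**Working it through.** **Plan's own figure.** There is no error rate to reproduce. The nearest figure is the 88 women of section 16.2, described as enough for moderate to large effects. At 80% power and two-sided 5%, the smallest detectable d is (1.96 + 0.84) × √(4(1 + ICC)/88): 0.60 at ICC 0, 0.68 at 0.3 and 0.73 at 0.5. The plan gives no number to compare with this, and the error-rate calculation does not depend on sample size.

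**Inputs from the documents.** Constructs: readiness, barriers, alcohol knowledge and strategies, FAPB. That is four as the SAP lists them, or five if knowledge and strategies are separated. Between-arm models per construct: two in the SAP. Post-baseline time at which the Stage 3 procedures assess controls before they receive the FMI: week 12 only.

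**Assumptions.** Two-sided 5% per test, which the 95% bands suggest but do not state; no true effect; correlation between test statistics from 0 to 0.8.

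**Step 1. One model, k contrasts.** If independent, the chance of at least one significant result is 1 − 0.95^k, and in the favourable direction only 1 − 0.975^k. With common correlation ρ, it is 1 − ∫ [Φ((1.96 − √ρ·u)/√(1−ρ)) − Φ((−1.96 − √ρ·u)/√(1−ρ))]^k φ(u) du. The favourable-direction version drops the second Φ term.

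| ρ | k = 4: two-sided (favourable) | k = 5: two-sided (favourable) |
|---|---|---|
| 0 | 18.5% (9.6%) | 22.6% (11.9%) |
| 0.5 | 15.6% (7.8%) | 18.3% (9.2%) |
| 0.8 | 11.4% (5.7%) | 12.7% (6.4%) |

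The range is 11–23% (6–12% favourable), against 5% (2.5%) for one named contrast.

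**Step 2. Both models, if they could be run.** The 2k test statistics were simulated as correlated normals (1,000,000 draws), with correlation ρb between constructs, ρw between the two models of one construct, and ρb × ρw otherwise.

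| Constructs | ρb | ρw | Two-sided | Favourable |
|---|---|---|---|---|
| 5 | 0 | 0.6 | 36.7% | 20.1% |
| 5 | 0.5 | 0.7 | 28.8% | 14.5% |
| 5 | 0.5 | 0.8 | 27.1% | 13.6% |
| 4 | 0.5 | 0.8 | 23.4% | 11.7% |
| 4 | 0.8 | 0.8 | 17.2% | 8.6% |

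The range is about 17–37%, and about half that in the favourable direction.

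**Step 3. Can both models be run?** On the Stage 3 schedule, wait-list women have no assessment matching the first post-intervention one and no six-wave series before they receive the FMI. Alcohol knowledge has no six-wave series in either arm. The strategy items refer to a personal list built partly during the FMI session, which controls have not yet had. So Step 1 is the case the documents support, and Step 2 is conditional.

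**Step 4. Selection of estimates (illustration).** Take 96 women (48 dyads) and an assumed within-dyad ICC of 0.3. The standard error of d is √(4 × 1.3/96) = 0.233. The expected largest of five null estimates correlated 0.5 is 1.163 × √0.5 = 0.82 standard errors, so d = 0.82 × 0.233 = 0.19. With ICC from 0 to 0.5 it is 0.17 to 0.21.

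**The case against.** The strongest reply is that this is a development study that says so. Feasibility comes before significance, effect sizes will carry 95% bands, and the SAP itself warns that small-pilot estimates are unreliable. No rule says that one significant result suffices; Aim 3 expects change across all the targets. All of that is true, and it limits the harm. It does not close the gap, because tests are promised, significance is predicted, and the estimates are meant to feed later studies.

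A second reply is that every goal is directional, so a significant harmful effect would not be claimed as success. That stands, and is why the favourable-direction rates are given.

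A third is that the SAP makes attitudes and behaviours joint targets, so choosing among them is a scientific decision. That also stands: the construct and score are for the investigators to choose.

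Three stronger readings are tempting but not supported:

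- A reader might count at least ten between-arm tests and quote a single rate such as 27%. Ten requires splitting knowledge from strategies and running models for which controls have no scheduled data. The 27% also needs one particular pair of correlations that the documents do not give.
- A reader might count every subscale and reach a much higher rate. The scores to be analysed are not fixed, and those for perceived barriers cannot be counted.
- A reader might take section 1.2 as stating a rival lead hypothesis. Its expectation, "We expect changes in readiness and other barriers to be associated with implementation of FAPBs", is the SAP's third primary goal, and it is nowhere ranked above the others.

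**Conclusion.** The point holds. The plan puts four or five constructs under unranked primary goals, with two between-arm models each, and gives no primary contrast or error control while committing to inferential tests. On the contrasts that the control schedule supports, the chance of at least one false significant result is about 11–23% (6–12% favourable). It would be about 17–37% only if both models could be run. These figures rest on an assumed two-sided 5%, no true effect, correlations of 0–0.8 between constructs and, for the second range, 0.6–0.8 between models. The goal 3 associations and any choice among several scores are not counted and could only add to them. For a pilot this is a gap in interpretation that should be closed before analysis; it does not invalidate the design.

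**What to change.** In the SAP, name one primary contrast: FMI versus wait list at week 12, on one pre-specified score, from the dyad-nested model with a 95% interval. Week 12 is the one post-baseline time at which the Stage 3 procedures give both arms an assessment before controls receive the FMI. FAPB implementation (goal 2) is the natural candidate. The investigators choose the score and should state its recall period, which needs to be the same in both arms.

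Then:

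- Label the other constructs, scores and models and the goal 3 associations secondary or exploratory, with 95% intervals and no significance claim. A Holm adjustment is optional in a pilot.
- Reword the prediction of significant change in Aim 3 to match.
- State that the planning effect for the next trial comes from the primary contrast.
- Reconcile the SAP's two between-arm models with the control schedule in the Stage 3 procedures and with the measurement times for alcohol knowledge and strategies in section 10.3.

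One named contrast returns the error rate to 5% two-sided (2.5% favourable). The cost is about a paragraph in the SAP and matching lines in the protocol, with no added participants or procedures. The downside is that a nominally significant non-primary result can no longer be claimed as showing that the FMI works.

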#### **Baseline Assessment**

*Demographic (baseline).* Demographic variables will be assessed, including sex, age, ethnicity, sexual orientation, family history of alcohol problems, living situation (with family, friends, alone, etc), work status, year in school, romantic relationships, and weight (for BAC calculations).

*Sexual Assault (baseline).* A revised version of the Sexual Experiences Survey (RSES; Koss et al., 2007; will be used to measure a spectrum of sexual victimization experiences. At baseline, lifetime experiences will be assessed. This will enable us to examine whether SA history affects intervention efficacy, or intervention response (e.g., guilt, blame, other possible iatrogenic effects) in exploratory analyses.

*Drinking history (baseline).* A variety of alcohol behaviors and related outcomes will be assessed. Using a grid-based average assessment measure, participants will report on typical weekly alcohol consumption over the past week (for relevant comparison of follow-up data) and past year (for descriptive purposes), including the average number of drinks consumed per occasion, and the average time over which drinks were consumed (for blood alcohol calculations). Harmful drinking outcomes will be assessed with the 48-item Young Adult Alcohol Consequences Questionnaire (YAACQ; [name] et al., 2006, 2007). We will also assess frequency of drinking in various contexts including parties, bars, etc. to assess patterns of exposure to high risk contexts.

*Relationship information (baseline).* We will assess the duration and origin of the friendship, as well typical amount of time spent together. Note that at baseline we will assess level of closeness to confirm eligibility. Dyads who do not identify one another as a "close friend" will be excluded from participation.

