#### **Friend-Based Assault Prevention Behavior Skills (FAPB)**

*Peer-Directed Bystander Behaviors for Sexual Assault Prevention (Baseline, bi-weekly).* We will use the 49-item Bystander Behaviors Scale for Friends (Banyard et al., 2014), which includes 4 subscales (1) the identification of sexual assault risk situations, (2) accessing resources, (3) planning ahead for risk situations, and (4) safety behaviors in risk settings. This measure will be adapted to include a broader

range of protective behaviors based on findings at Stage 1, and some of the items that refer to intimate partner violence will need to be reworded to assess sexual violence. Participants will complete this measure with respect to their target friend (i.e., did they do this for their friend) and also for themselves (i.e., did their friend do this for them?).

*Sexual Assault-Related Protective Behaviors (baseline, bi-weekly for all drinking occasions).* A measure developed by Armstrong et al., the Women's Peer-Directed Protective Strategy questionnaire (WPPS) will be used to evaluate assault-specific protective behaviors. This 24 item measure includes items such as, "I try to be aware and monitor where my friends are at all times," and, "I watch out for my friends in an attempt to keep them away from (risk) situations". Participants will complete this measure for their target friend (i.e., did they do this for their friend?) and also for themselves (i.e., did their friend do this for them?). Participants will be asked to rate frequency and how effective they perceived each behavior to be. They also will rate how they felt about it when they or their friend engaged in the behavior or did not engage in the behavior (when there was an opportunity) using a brief checklist of positive and negative feelings (e.g., good, relieved, safe, guilty, angry, scared). This will be based on information from qualitative participant interviews at earlier stages.

We also will assess whether the intervention resulted in unanticipated or adverse consequences, such as placing undue stress on a member of the dyad, or straining the friendship.

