**18.2 Describe any safety endpoints.**

Response: As described above, safety endpoints involve identified distress or danger to a participant. It is important to note that our procedures are designed to balance reasonable measures to maintain participant safety, while at the same time not discouraging accurate and truthful reporting on the part of participants. As described above, policies such as those involving the implementation of Title IX have been developed with this specific challenge in mind. Wanton reporting of every distressing event has

the potential not only to have a deleterious effect on the study, but also can be iatrogenic for the participants themselves.

*18.3 Describe how the safety information will be collected (e.g., with case report forms, at study visits, by telephone calls with participants).*

Response: See above.

*18.4 Describe the frequency of safety data collection.*

Response: As is outlined in the description of our study approach above, we will collect data pre- and post-intervention, and then at follow-ups. Data will be reviewed for safety concerns at each data collection occasion.

*18.5 Describe who will review the safety data.*

Response: Drs. [name] and [name] and associated project staff (project manager, graduate student) will review the safety data. Requests for contact will come to [name], and she will oversee these procedures.

*18.6 Describe the frequency or periodicity of review of cumulative safety data.*

Response: Safety reviews will be ongoing throughout the course of the study. Please see descriptions above.

*18.7 Describe the statistical tests for analyzing the safety data to determine whether harm is occurring.*

Response: There are no statistical tests to determine safety.

*18.8 Describe any conditions that trigger an immediate suspension of the research.*

Response: The research would be suspended if, in the highly, highly unlikely event, it was determined that the research was leading to immediate and identifiable distress or danger to participants.

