## 20.0 Risks to Subjects

### 20.1 List the reasonably foreseeable risks, discomforts, hazards, or inconveniences to the subjects related to their participation in the research.

**Response:** Risks posed to participants in the present study are minimal. Evidence shows that assessments of sexual assault and related experiences may be conducted without serious deleterious psychological effects. Some participants may experience minor emotional discomfort or embarrassment in responding to questions pertaining to potentially sensitive topics such sex or sexual assault, or even substance use. This could occur during completion of self-report assessments, or during individual interviews. However, such discomfort is relatively rare, and is almost always mild and transient. Our labs have been conducting both in-person and online assessments of these phenomena for more than a decade and are well equipped to manage participant needs in the event that distress occurs (see below).

As this dyad-based intervention focuses on motivating a sense of agency for action, through enhancement of personal responsibility and relationship between friends, another potential risk pertains to inadvertent, iatrogenic effects of the intervention. For example, in cases where sexual victimization occurs to one of the dyad members – or even if it doesn't- the other member of the dyad may believe that somehow she is to blame. We plan to assess such effects carefully, with an eye toward both (1) modification of the intervention to decrease such iatrogenic effects, and also (2) ensuring the wellness of the participants enrolled in our study. Efforts to address the first of these issues (future intervention modification) are described in the body of the proposal. To address specific participant wellness concerns, here we outline several steps that we will take in the "Adequacy of Protection Against Risk" section, below.

Lastly, because our study focuses on high-risk (i.e., heavy drinking) women, it is possible and perhaps even likely that women will experience some kind of event that falls along the spectrum of assault behaviors during the course of follow-up. Though this assault would not be as a result of the intervention itself, it is a risk that our participants could incur during the period of follow-up and as such, is something that we have planned to address in our procedures. These procedures are described below.

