guilt and blame. Participants will be encouraged to discuss these concerns with interventionists at follow-up, with one of the two PIs, or to seek out additional support, available through our referral list. Third, as follow up interviews now have specific measures and interview questions that will serve as “flags” for our interventionists to assess for signs of distress. In cases where distress is indicated, interventionists and follow-up interviewers will have a protocol as to specific follow-up questions, and a link to referral resources. Finally, as we have done in previous work, our online assessments will have a “**REQUEST for CONTACT**” button. Participants are instructed to click on this button if they are distressed and would like to talk to a member of the project staff. Clicking this will generate an e-mail to our staff, and [name] (UB), who is a clinical psychologist, will contact the participant within two business days.

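### Guilt is a harm the protocol names and rates, but the SAP plans no between-arm or change analysis of it; relationship quality is the only modelled outcome it ties to iatrogenic effects

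*Combined protocol and SAP*

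**What the plan says.** Protocol 1.1 and 4.1 list iatrogenic effects among the things the study will examine. Protocol 20.1 gives the leading example: if one friend is victimised, or even if not, "the other member of the dyad may believe that somehow she is to blame". On such effects it says "We plan to assess such effects carefully". Protocol 20.2 has the debriefing describe possible effects including "guilt and blame. Participants will be encouraged to discuss these concerns with interventionists at follow-up".

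Protocol 10.3 describes what is collected:

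- **Feelings checklist.** Under "Sexual Assault-Related Protective Behaviors (baseline, bi-weekly for all drinking occasions", women rate how they felt when they or their friend did or did not act, "using a brief checklist of positive and negative feelings (e.g., good, relieved, safe, guilty, angry, scared".
- **Adverse consequences.** The same section asks about undue stress and strain on the friendship.
- **End of Treatment Questionnaire.** Treatment components are rated from -3 (greatly harmful) to +3 (greatly helpful).
- **Assault history.** The baseline section says it will be examined in relation to "intervention response (e.g., guilt, blame, other possible iatrogenic effects) in exploratory analyses".

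On analysis, the SAP's outcome section says "Increases or decreases in relationship quality as a function of the intervention would suggest either a positive impact on dyadic relationships or iatrogenic effects". Its between-arm models cover perceived barriers, readiness, alcohol knowledge and strategies, and protective behaviours; its change models cover the same constructs. Participant evaluations are summarised descriptively under feasibility and fidelity, and exit interviews are analysed qualitatively. Protocol 16.1 (Aim 3) matches the SAP on all of this. Protocol 18.7 adds: "There are no statistical tests to determine safety".

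**The concern.** Protocol 20.1 connects the risk of self-blame to the way the intervention works, which is by strengthening personal responsibility between friends. A harm that could follow from the active ingredient deserves an estimate by arm.

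Relationship quality does not stand in for it. A woman may feel guilty and still rate the friendship as close, so relationship quality could hold steady or improve while guilt rises. If the plan is followed as written, that pattern would appear in no planned comparison of FMI with wait-list, although the pilot exists to shape the next trial and the relevant item is collected.

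**Working it through.** The plan states no figure on this point, so the main check is a trace of each harm source from measurement to analysis.

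| Source (protocol 10.3) | Planned analysis | Randomised contrast? |
|---|---|---|
| 'Guilty' on the feelings checklist, baseline and bi-weekly | None in 16.1 or the SAP | No |
| Guilt and blame as response, by assault history | Exploratory, in the measures section only; no instrument or model named | No; it asks about assault history |
| Adverse-consequence questions | None named | No |
| End of Treatment harm ratings | Descriptive, as participant evaluations | No; they are reactions to the intervention |
| Exit interview | Qualitative | No |
| Relationship quality | Change as a function of the intervention | Yes |

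The SAP does mention assault history as a predictor of change, but its examples are perceived barriers and skill implementation, not guilt.

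**Is a randomised contrast possible?** Yes, at one time point. Stage 3 Procedures assess controls at baseline and at 12 weeks, before they receive the FMI, with measures that mirror those of the FMI arm.

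**How precise would it be?** Inputs from the documents: 24 dyads per arm, so 24 × 2 = 48 women per arm (Stage 3, Aim 3). Protocol 16.2 instead gives 88 women, or 44 per arm, and the timeline gives 92. Assumption: a within-dyad intraclass correlation (ICC) of 0 to 0.3, as the documents give none. The design effect for pairs is 1 + ICC.

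1. Effective n per arm at ICC 0.3: 48/1.3 = 36.9; with 44 women, 44/1.3 = 33.8.
2. Two-sided 95% upper limit if no FMI woman reports guilt, 1 − 0.025^(1/n):
   - 48 women: 1 − 0.025^(1/48) = 7.4%; at ICC 0.3, 1 − 0.025^(1/36.9) = 9.5%.
   - 44 women: 1 − 0.025^(1/44) = 8.0%; at ICC 0.3, 1 − 0.025^(1/33.8) = 10.3%.
3. Illustration with assumed rates of 20% (FMI) and 5% (wait-list), ICC 0.3: difference 0.15; SE = √(0.20×0.80/36.9 + 0.05×0.95/36.9) = 0.075; 95% CI 0.15 ± 1.96×0.075 = 0.003 to 0.297. The control arm would expect only 0.05 × 48 = 2.4 events, so this normal approximation is rough.
4. If the item is scored as a graded rating, the 95% CI half-width is 1.96×√(2/n) SD. At 48 per arm this is 0.40 SD (ICC 0), 0.46 SD (ICC 0.3) and 0.49 SD (n = 48/1.5 = 32 at an assumed ICC of 0.5).

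The contrast can be estimated, but only with wide limits.

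**The case against.** Several stronger readings are tempting, and the documents do not support them.

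- *Guilt is analysed nowhere.* A reader might infer this from the SAP alone. The baseline section of 10.3 does plan exploratory work naming guilt and blame. It is under-specified and not carried into the SAP, but it exists.
- *Relationship quality is the only harm evidence.* It is the only modelled outcome tied to iatrogenic effects. The numeric harm ratings are summarised descriptively and help guide changes to the intervention, which is one of the two purposes 20.1 gives for assessing such effects. Exit interviews are analysed too.
- *The trial would declare no harm if friendships held up.* No section says so. The SAP says only what a rise or fall in relationship quality would suggest.
- *Self-blame is measured.* Only 'guilty' appears, as an example item on a checklist tied to protective behaviours on drinking occasions. The checklist also depends on interviews from earlier stages, so its items are not final. It captures the harm described in 20.1 only in part.
- *Protocol 18.7 shows that harms go unwatched.* It answers a question about safety tests. Sections 18 and 20.2 describe review at each data collection, distress flags and emergency procedures. These protect individuals, though they do not estimate an arm difference.

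It is also fair to say that this is a feasibility pilot and that any estimate will be imprecise. That stands. But the plan already chooses effect sizes with 95% bands over significance, and a harm estimate fits that approach.

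**Conclusion.** The point holds in this form: a harm that the protocol names, and partly measures in both arms, has no between-arm or change analysis in the SAP or protocol 16.1. Relationship quality is the sole modelled outcome linked to iatrogenic effects, and the other harm sources yield no randomised comparison.

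What is lost is a week-12 estimate. It would be a coarse one: with no reports among 48 FMI women, rates up to about 7% to 10% would remain compatible with the data. That range rests on the assumed ICC of 0 to 0.3 and on full follow-up; the smaller sample in 16.2 widens it slightly. The gap is worth closing because doing so costs little, not because the pilot could settle the question.

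**What to change.** Add a short harms paragraph to protocol 16.1 and the SAP, using collected data only.

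1. Make 'guilty' a separate exploratory harm outcome, and add a blame item only if the final checklist contains one. Report it by arm at week 12 as number and percent of all women assessed, with a difference and 95% CI that allow for dyads and, where counts permit, adjust for the baseline rating. Specify the same recall window in both arms: FMI women report on the time since their last survey, while the control window is not stated. Do not pool it with 'scared' or 'angry', which may reflect a risky occasion or a friend's behaviour.
2. Report its frequency descriptively at each bi-weekly survey after the FMI, and by assault history as 10.3 promises. Label any figure restricted to women reporting an opportunity to intervene as descriptive. Opportunity arises after randomisation, and the FMI teaches risk recognition, so that subgroup is not an arm comparison.
3. Report the number and percent of women with any End of Treatment component rated below 0, or with any adverse-consequence report.
4. State that relationship quality is one of several iatrogenic measures, that the checklist captures self-blame only in part, and that intervals this wide cannot support a conclusion of no harm.

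The cost is SAP wording and one short table, with no new data or visits. The downside is a few more imprecise descriptive estimates.
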